9.2. Dose Modifications

Dose modifications as reported on the Drug Log, Drug Interruption Log, and Drug Overdose Log eCRFs will be used in summaries. Patients with any IP drug overdose, any IP drug interruption, any IP drug interruption of at least 14 days will be summarized by number and percentage, respectively. The total number of drug overdoses and total number and percentage of AEs as a

result of overdose will be summarized. Duration of drug interruption will be summarized descriptively. The number and percentage of patients will be summarized by duration of drug interruption category (<7 days, 7-<14 days, ≥14 days). The total number of drug interruptions and reasons for interruption will be summarized.

9.3. Treatment Compliance

Treatment compliance for IP will be calculated for each patient by taking into account whether a patient takes all doses of investigational drug as instructed.

For subjects undergoing dose escalation, the total number of capsules expected to be taken by a patient is calculated as follows:

Last dose date – first dose date + 4 (+ 1 to account for the number of days between those dates inclusive and +3 to account for 3 extra capsules taken during dose escalation on Study Days 5-7)

If a patient discontinues trial during or prior to Study Days 5-7 during which 2 capsules per day are taken, then the number of capsules expected will be adjusted accordingly. For example, if discontinuing on Day 5, then +1; on Day 6, then +2; on Day 7 or after, then +3.

The total number of IP capsules actually taken by a patient is defined as the total number of capsules dispensed – total number of capsules returned during IP, as reported on the Drug Log eCRFs. The overall IP treatment compliance (%) will be calculated as the total number of IP capsules taken divided by the total number of IP capsules expected and multiplied by 100. If the bottle is not returned by the patient at a visit, then the subject is considered to have returned zero pill from the unreturned bottle in the treatment compliance calculation.

The total number of IP capsules expected, actually taken and overall IP treatment compliance will be calculated and summarized after taking into account all such visits at which the bottle is not returned.

Additionally, the number and percentage of patients will be summarized by category (<50%, 50% to <60%, 60% to <70%, 70% to <80%, 80% to 100%, and >100%). Two additional categories (<80% and >120%) will also be included.

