12.1.11. Clinical Laboratory Evaluations

The central laboratory will analyze the samples. Further details of the procedures to be followed for sample collection, storage, and shipment will be documented in a laboratory manual.

Repeat testing for protocol required laboratory tests are to be analyzed by the central laboratory. Additional testing may be performed at the discretion of the Investigator and analyzed by the local laboratory. Approval from the Medical Monitor must be obtained if retest is required to be repeated > 2 times.

- Hematology: Red blood cell count, total and differential WBC count (basophils, eosinophils, lymphocytes, monocytes, and neutrophils), platelet count, Hb, hematocrit, mean corpuscular volume, mean corpuscular hemoglobin, and mean corpuscular hemoglobin concentration. Total WBC count and all differential WBC counts will be blinded information for the treating Investigator after initiation of investigational drug. Of note, WBC, basophil, eosinophil, lymphocyte, monocyte, and neutrophil counts will not be disclosed to preserve the blind.

During the treatment period, WBC differential results will be available to an unblinded medical reviewer not directly participating in study conduct. Reductions in ALC levels is a known pharmacodynamic effect of RPC1063. If any of the following results are observed, the Investigator will be notified and asked to repeat the laboratory tests within approximately 7 days:

- Absolute neutrophil count (ANC) < 1000 cells/ μ L
- Absolute lymphocyte count (ALC) < 200 cells/ μ L

If the ANC is confirmed below the 1000 cells/ μ L limit, the Investigator will be requested to closely monitor for risk of serious infection and institute appropriate follow-up, at the discretion of the Investigator.

If the ALC is confirmed below the 200 cells/ μ L limit, the Investigator will temporarily discontinue investigational drug and then consult with the Medical Monitor. Laboratory testing will be repeated weekly during the treatment period until the ALC > 500 cells/ μ L. When ALC has returned to > 500 cells/ μ L, the treatment may be reinitiated at the Investigator's discretion (see [Section 9.1.3](#) for instructions on resuming treatment after missing doses).

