5.2. Per-Protocol (PP) Population

The PP population will consist of all patients in the ITT population who adhered to the protocol with no major protocol deviation that potentially affects efficacy in the induction period. This population will be used in the sensitivity analysis of clinical remission and additional analysis of clinical response to evaluate the influence of major protocol violators and protocol deviators on the primary results. Patients will be excluded from this population if they meet any of the following reasons, which will be documented prior to database snapshot:

- Investigational drug noncompliance > 20% (i.e., overall IP drug compliance not in [80%, 120%])
- Receiving incorrect investigational drug leading to a treatment change for more than 1 week in the IP
- Prolonged concomitant use of systemic corticosteroids (except topical use) > 7 days before Week 10, for treatment of disease other than UC, at a total daily dose higher than the maximum dose taken between the Screening and Baseline

- Concomitant use of protocol-specified excluded medication that potentially affects efficacy for unrelated comorbid condition

█ [REDACTED]

- Violation of key entry criteria (i.e., inclusion criterion #4 [Have active UC defined as Mayo score of 6 to 12 inclusive, with endoscopic subscore of ≥ 2 , a rectal bleeding score of ≥ 1 , and a stool frequency score ≥ 1], exclusion criterion #2 [Diagnosis of Crohn's disease or indeterminate colitis or the presence or history of a fistula consistent with Crohn's disease or microscopic colitis or radiation colitis or ischemic colitis], and primary non-responders to 2 or more biologic agents approved for the treatment of UC)

The PP population will be fully identified and documented prior to induction treatment is unblinded. Patients excluded from PP population and the reason for exclusion will be listed. Similar to the ITT population, PP patients in Cohort 1 who received an incorrect investigational drug from that which was randomized will be summarized in the treatment group according to the intended randomization. Patients in Cohort 1 who were randomized with a misreported stratum will be analyzed according to their original [misreported] stratum.

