9. STUDY TREATMENTS AND EXTENT OF EXPOSURE

All patients will initiate investigational drug via a 7 day dose escalation regimen starting with RPC1063/ozanimod HCl 0.25 mg (equivalent to ozanimod 0.23 mg) or matching placebo (matching placebo for Cohort 1 only) on Days 1 to 4 and RPC1063/ozanimod HCl 0.5 mg (equivalent to ozanimod 0.46 mg) once daily or matching placebo on Days 5 to 7. On Day 8, patients will receive the final dose level (1 mg once daily or matching placebo) for 9 weeks. Patients will record whether they took the daily dose of medication in a diary that will be reviewed periodically by site staff and the Site Monitor.

There will be an individual investigational drug accountability record for each patient and the Investigator should maintain accurate records of the disposition of all investigational drug supplies received during the trial. The number of capsules and date investigational drug supplies are dispensed to the patient and returned by the patient are reported on the Drug Log eCRFs. Overdoses are reported on the Overdose Log eCRF and drug interruptions are reported on the Drug Interruption Log eCRF.

A summary of extent of exposure to IP treatment for the Safety population will include overall treatment duration, dose modifications, and treatment compliance, as defined in Section 9.1, Section 9.2, and Section 9.3. The summary will be presented by treatment/cohort and in Total RPC1063 1 mg. Individual data listings will also be provided.

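### SAP 9.3 counts protocol-ordered dosing holds as missed capsules, so an adherent patient held 15 days or more in a 70-day induction and then restarted meets the Per-Protocol exclusion

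*SAP*

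**What the plan says.** **Aim and denominator.** SAP 9.3 says induction compliance is calculated "by taking into account whether a patient takes all doses of investigational drug as instructed". Expected capsules are "Last dose date – first dose date + 4". The constant covers the inclusive day count plus three extra capsules on Days 5 to 7, and is cut back for very early stops ("if discontinuing on Day 5, then +1; on Day 6, then +2; on Day 7 or after, then +3"). No term removes interruption days, and SAP 9.3 does not define the last dose date.

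**Numerator.** Capsules taken are the "total number of capsules dispensed – total number of capsules returned during IP". A bottle not brought back counts as nothing returned.

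**The hold.** Under Protocol 12.1.11, if a lymphocyte count below 200 cells/µL is confirmed, "the Investigator will temporarily discontinue investigational drug and then consult with the Medical Monitor". Counts are then repeated weekly until above 500, after which restarting is at the Investigator's discretion. The same section describes the lymphocyte fall as a known effect of the drug.

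**Consequence.** SAP 5.2 lists overall induction compliance outside 80% to 120% among the reasons for which a patient will be excluded from the Per-Protocol set. SAP 10 says such exclusions are settled case by case, blinded. Protocol 13.2.2 says only that patients may be excluded.

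**Data at hand.** SAP 9 notes that "drug interruptions are reported on the Drug Interruption Log eCRF". SAP 9.2 tabulates interruptions, their duration and their reasons, but SAP 9.3 makes no use of them.

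**The concern.** A patient who stops drug because the protocol requires it has followed instructions, yet the formula scores each such day as a missed capsule. The Per-Protocol analysis is meant to show the influence of protocol violators, and these patients are not violators. Because the trigger is a drug effect, any resulting exclusions would fall almost entirely on the active arm, and the by-arm table of patients below 80% would make that arm look less adherent than it was.

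The rule may also fail to track exposure. A patient who restarts after a long hold can be excluded, while one held from the same day who never restarts, and so takes fewer capsules, can stay in. Whether that happens depends on the undefined last dose date.

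**Working it through.** **1. Reproduce the SAP's count.** The schedule is one capsule on Days 1 to 4, two on Days 5 to 7, and one from Day 8. For 70 days this gives 4 + 6 + 63 = 73; the SAP formula gives 69 + 4 = 73. Counting day by day, the two agree for every last-dose day from 1 to 90. The formula is right for uninterrupted dosing.

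**2. Hold and restart within induction.** With E capsules expected and a hold of h days after Day 8, a patient who takes every other dose scores (E − h)/E. The Week 10 visit window is Day 70 ± 10 (Protocol Table 1), so lengths of 60, 70 and 80 days are shown.

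| Induction length | E | Longest hold staying at or above 80% | Shortest hold falling below 80% |
|---|---|---|---|
| 60 days | 63 | 12 days: 51/63 = 81.0% | 13 days: 50/63 = 79.4% |
| 70 days | 73 | 14 days: 59/73 = 80.8% | 15 days: 58/73 = 79.5% |
| 80 days | 83 | 16 days: 67/83 = 80.7% | 17 days: 66/83 = 79.5% |

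At 70 days, a 7-day hold gives 66/73 = 90.4% and a 21-day hold 52/73 = 71.2%. If a restart repeated the escalation (an assumption, adding 3 capsules taken), the thresholds would become 16, 18 and 20 days. Other missed doses lower the thresholds; unreturned bottles raise them.

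**3. Hold and no restart.** Take the last capsule on Day 42.
- If the last dose date is the last capsule taken: expected = 41 + 4 = 45, and 45/45 = 100%.
- If the denominator runs to Day 70, as it would for a maintenance entrant under the SAP 9.1 treatment-duration rule (which ends induction the day before maintenance dosing): 45/73 = 61.6%.

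**4. Time available.** Scheduled on-treatment hematology in induction is at Week 5 (Day 35 ± 5) and Week 10, and a low count is repeated within about 7 days. A hold triggered by the Week 5 sample would therefore start near Day 42 (assumption). That leaves about four weeks in which both a hold of 15 days or more and a restart must fall.

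**5. How many patients.** Protocol Appendix 3 gives 3.3% below the lymphocyte limit on 0.92 mg in the Phase 3 multiple sclerosis program.
- Planned active arm: 0.033 × 400 = 13.2.
- Reported Cohort 1 of 645 at 2:1, about 430 active: 0.033 × 430 = 14.2.

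This is a loose ceiling. It comes from another disease, not from a 10-week course, and it counts everyone below the limit. Only patients with a confirmed low count, a long enough hold and a restart before Week 10 are affected.

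**6. Effect at the ceiling.** At the planned 16% remission rate, 64 of 400 active patients remit. Removing 13 leaves 387:
- none of the 13 a remitter: 64/387 = 16.5%;
- half remitters: 57.5/387 = 14.9%;
- all 13 remitters: 51/387 = 13.2%.

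If the 13 remit at 16%, the rate does not move.

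**The case against.** **Compliance is defined by quantity.** Protocol 9.7 uses the same 80% and 120% limits with no exception by reason, and a ratio that ends at the last dose is a usual measure of adherence while on treatment. Early stopping is reported in disposition, and missing Week 10 data are handled by non-responder imputation. This stands as an account of where the limits come from. It does not answer the mismatch with SAP 9.3's own stated aim.

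**Exclusion may not be automatic.** SAP 10 and Protocol 13.2.2 leave room for judgment, and the same exposure summary shows interruptions with their reasons. That softens the point. But SAP 5.2 is worded as mandatory, so the texts conflict, and white-cell results are withheld before unblinding (SAP 6.7), so a blinded reviewer may see little beyond a low percentage.

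**Reach is small.** This stands in full. A reader might infer that every patient held and restarted becomes noncompliant; holds of 7 and 14 days in a 70-day course do not cross 80%. A reader might also infer that never-restarted patients always score about 100%; that depends on a date the SAP does not define. Nor are all patients with a low lymphocyte count affected, because the low count must be confirmed, the hold long and the restart timely. Suspension for a positive urine pregnancy test is a weak further example: a serum test follows promptly, and confirmed pregnancy ends treatment, so a long hold followed by restart is unlikely.

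**Unseen text.** One Per-Protocol exclusion item is blacked out and the SAP appendices are not available, so a rule on holds there cannot be ruled out.

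**Conclusion.** The point holds in limited form. On the readable text, SAP 9.3 scores protocol-ordered interruption days as missed capsules, and a restarted hold of at least 13, 15 or 17 days (inductions of 60, 70 or 80 days) puts an otherwise adherent patient below 80%. The treatment of never-restarted patients is undetermined, at 100% or about 62%.

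The distortion is related to arm but small. About 13 to 14 active patients is a loose upper bound, and the real number may be close to zero. Even at that bound the active Per-Protocol remission rate would lie between 13.2% and 16.5% against 16%, and the low end requires every removed patient to be a remitter. The documents do not support reading this as a material bias in the efficacy result: the primary analysis uses the ITT population, and the Per-Protocol analyses are supportive without Type I error control. What is affected is the Per-Protocol set and the compliance table. The conclusion assumes otherwise perfect adherence, full bottle returns, and no relevant rule in the unavailable text. It is a worthwhile clarification, not a threat to the trial's conclusions.

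**What to change.** 1. In SAP 9.3, subtract protocol-required interruption days, taken from the Drug Interruption Log, from expected capsules, and add any extra capsules the patient is instructed to take at restart. A 21-day hold in 70 days then scores 52/52 = 100% instead of 71.2%.
2. Define the last dose date separately for patients who do and do not enter maintenance, and say whether the SAP 9.1 end date applies to compliance.
3. Reconcile the mandatory wording of SAP 5.2 with the case-by-case wording of SAP 10, and state whether a protocol-required hold can lead to Per-Protocol exclusion.
4. If low exposure is meant to exclude patients, state it as its own criterion and apply it alike to restarted and never-restarted patients.

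The cost is SAP wording and one programming step on data already collected. The downside is a small blinded classification step: each interruption must be labelled protocol-required or not before unblinding. Since a lymphocyte hold hints at active treatment, the label should be a plain yes or no that discloses no white-cell results. No clinical rule changes.

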10. PROTOCOL DEVIATIONS/VIOLATIONS

Deviations and violations from the protocol will be recorded appropriately. Protocol deviations will be classified into, but not necessarily limited to, the following categories:

- Excluded concomitant medication
- Informed consent
- Other/GCP issue
- Randomization procedure
- Selection criteria not met (i.e., violation of inclusion/exclusion criteria)
- Serious adverse event reporting
- Study procedure
- Treatment deviation
- Visit scheduling

Classification of deviations as major protocol deviations/violations and decisions regarding exclusion of patients from the PP will be decided on a case-by-case basis without knowledge of the treatment assigned and before database lock or Cohort 1 unblinding. Major protocol deviations will be presented in a summary table by protocol deviation category. All protocol deviations will be listed. Major protocol deviations that exclude patients from the PP population will be summarized separately.

Besides the listing for patients excluded from the PP population with reason as specified in Section 5.2, a separate listing will be created for patients who have met TFR during IP and thus excluded from PP population. This listing will include the date and study day of their first occurrence of confirmed TFR, and relevant description (e.g., medication name, indication, dose/frequency, Baseline dose/frequency, duration of use, or medical procedure name). This listing will also include the date and study day of their first IP dose, and the date and study day of their W10 endoscopy (if available). This listing will be reviewed, confirmed, and finalized before database lock or Cohort 1 unblinding. See detail about treatment failure rules data review in [Appendix 1.3](#).

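### SAP 9.3 counts every capsule in an unreturned bottle as taken, so some early stoppers score above 120% and some under-compliant completers score 80% or more, which can misclassify Per-Protocol membership.

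*SAP*

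**What the plan says.** SAP 9.3 (Treatment Compliance) builds the overall Induction Period score from three rules.

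- Expected capsules are "Last dose date – first dose date + 4". This covers the inclusive day count plus three extra capsules on Days 5 to 7. For very early stops the extra term is adjusted: "if discontinuing on Day 5, then +1; on Day 6, then +2; on Day 7 or after, then +3".
- Capsules taken are "defined as the total number of capsules dispensed – total number of capsules returned during IP", using the Drug Log eCRFs.
- For a bottle not brought back, "then the subject is considered to have returned zero pill from the unreturned bottle in the treatment compliance calculation".

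SAP 5.2 (PP Population) uses the score as an exclusion rule, with limits of 80% and 120%: "Patients will be excluded from this population if they meet any of the following reasons". SAP 10 describes PP exclusion decisions differently, as "decided on a case-by-case basis without knowledge of the treatment assigned". Protocol 13.2.2 also words exclusion as something that may happen.

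SAP 5.2 gives the PP set two uses: a sensitivity analysis of clinical remission and an additional analysis of clinical response. SAP 9.3 also tabulates compliance by category, with rows for below 80% and above 120%.

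**The concern.** The numerator and the denominator treat an unreturned bottle inconsistently. The numerator takes its full content, which may cover several weeks. The denominator ends on the last dose date. A patient who stops part-way through a bottle and does not return it is credited with weeks of capsules over a few days. A completer who skipped doses and lost the bottle is credited with the skipped doses.

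SAP 9.3 has no cap, no category for an unevaluable score and no cross-check against another intake record. The 80% to 120% limits are therefore applied to numbers that can be artefacts in either direction.

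What is at stake is the PP comparison. Under non-responder imputation (NRI), an early stopper with no Week 10 data counts as a non-remitter in ITT. If the same patient drops out of PP for apparent over-compliance, the PP remission rate in that arm rises. If stopping without returning the bottle differs by arm, so does the shift. The analysis could then lose adherent patients and keep real deviators, although its purpose is to show how much deviators matter.

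**Working it through.** **Reproducing the denominator.** Protocol 9.1.1 gives one capsule a day on Days 1 to 4, two a day on Days 5 to 7 and one a day from Day 8. To Day 70 that is 4×1 + 3×2 + 63×1 = 73. The SAP formula for a last dose on Day d ≥ 7 is d + 3, also 73 at Day 70. A direct count from the regimen agrees with the formula, including its early-stop adjustment, for every stop day from 1 to 90. The denominator is correct, so the problem lies in the numerator.

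**Assumptions.** The documents give no bottle size. I assume one bottle at each of visits I 1 and I 2. With no overage these hold 38 capsules (35 days + 3) and 35 capsules. With enough to cover the visit windows in Protocol Table 1 (Day 35±5, Day 70±10) they hold 43 and 50.

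**Early stoppers, first bottle not returned.** Score = bottle size / (d + 3).

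| Last dose | Expected | 38 capsules | 43 capsules |
|---|---|---|---|
| Day 7 | 10 | 380.0% | 430.0% |
| Day 14 | 17 | 223.5% | 252.9% |
| Day 21 | 24 | 158.3% | 179.2% |
| Day 28 | 31 | 122.6% | 138.7% |
| Day 29 | 32 | 118.8% | 134.4% |

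The score exceeds 120% up to Day 28 with 38 capsules and up to Day 32 with 43. Any single bottle that lasts to Week 5 holds at least 38, so Day 28 is a minimum under the one-bottle assumption.

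**Early stoppers, first supply of 38 fully used, second bottle not returned.** Score = (38 + second bottle) / (d + 3).

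- With 35 capsules, Day 40 gives 73/43 = 170%, Day 57 gives 73/60 = 121.7% and Day 58 gives 73/61 = 119.7%. Stops on Days 36 to 57 exceed 120%.
- With 50 capsules, Day 70 still gives 88/73 = 120.5%. A fully adherent completer who loses only the second bottle would then be excluded.
- The result depends on first-bottle intake. If 30 of the 38 were taken and 8 returned, the score is (30 + 35)/(d + 3). That is 65/54 = 120.4% at Day 51 and 65/55 = 118.2% at Day 52.

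**Under-compliant completers (Day 70, expected 73, bottles of 38 and 35).**

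- Even 70% intake, first bottle lost: (38 + 0.7×35)/73 = 62.5/73 = 85.6%. Second lost: (0.7×38 + 35)/73 = 61.6/73 = 84.4%. Both stay in PP.
- First bottle fully taken, half of a lost second bottle taken: true intake (38 + 17.5)/73 = 76%, scored 73/73 = 100%.
- Even 50% intake, first bottle lost: 55.5/73 = 76.0%. Second lost: 54/73 = 74.0%. Both are still excluded.
- Even 50% intake with bottles of 43 and 50, one lost: 60.5/73 = 82.9% or 69/73 = 94.5%. Both stay in PP.

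**Effect on the PP rate, illustration only.** At the Protocol 13.1 planning rate, 16% of 400 is 64 remitters. Removing 5% of the arm (20 patients, assumed), all non-remitters, gives 64/380 = 16.8%. The documents do not give the number who would be affected.

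**The case against.** Several points on the other side stand.

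- **The primary analysis is ITT with NRI (SAP 6.1.1).** Compliance does not enter it. The PP analyses are supportive and outside Type I error control (SAP 6.1.2).
- **Non-return may be uncommon.** Protocol 9.7 has capsules collected at each visit, and Protocol 8.4 asks discontinuers to complete an Early Termination visit. No document gives a non-return rate or shows that it differs by arm.
- **SAP 10 provides blinded case-by-case decisions on PP exclusion.** A reviewer could spare an implausible score of 224%. But SAP 5.2 says such patients will be excluded, SAP 10 gives no criterion for unreturned bottles, and a falsely normal 85% or 100% gives the reviewer nothing to notice.
- **One exclusion item in SAP 5.2 is redacted.** Some early stoppers may leave PP for another reason, and the documents do not let us see this.

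A reader might also infer stronger statements that the documents do not support.

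- *Early stoppers in general score above 120%.* Only those who do not return the bottle can. With no overage, stops on Days 29 to 35 and 58 to 69 stay at or below 120%.
- *Every stop on Days 36 to 57 exceeds 120% whatever was taken.* The Day 51 limit above shows that it depends on first-bottle intake.
- *Any poor taker who loses a bottle scores 100%.* With no overage this needs all bottles lost, or every missed dose in the lost bottle. The even 50% taker who loses one is still excluded.
- *The formula creates false overdoses.* SAP 9.2 summarises overdoses from their own log. SAP 5.2 calls this noncompliance.

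**Conclusion.** The concern holds in a limited form. Followed as written, SAP 9.3 and 5.2 can remove from PP some early stoppers who took no extra capsules, and can keep some completers whose true intake was below 80%. The mechanism follows from the text alone. The sizes rest on assumed bottle counts, chiefly one bottle per dispensing visit. Under that assumption, an unreturned first bottle gives a score above 120% for any stop up to Day 28 at least. The second-bottle range and the scores for under-compliant completers move with overage.

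The consequence is possible distortion of the PP analysis of clinical remission, the PP analysis of clinical response and the compliance table. It would be greater if non-return differs by arm. The documents do not show how often it would occur, and the ITT primary result does not depend on it. It is worth correcting because the PP analysis is a prespecified check on the primary endpoint and the correction is inexpensive.

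**What to change.** Amend SAP 9.3 and 5.2 before Cohort 1 is unblinded.

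1. For an interval with an unreturned bottle, take intake from the daily dosing diary (Protocol 9.7, SAP 9).
2. If the diary is missing, treat intake in that interval as unknown. Compute a lower bound (none taken) and an upper bound (all taken, capped at the number expected in that interval).
3. Exclude from PP for under-compliance only if the upper bound is below 80%. Do not exclude for a score above 120% when the excess comes only from an unreturned bottle.
4. Report by arm how many patients are affected, and repeat the PP analysis without those whose bounds straddle 80%.

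In the worked cases with bottles of 38 and 35, the Day 40 stopper has bounds 38/43 = 88% and 43/43 = 100% and is kept. The even 50% taker who loses one bottle has an upper bound of 76.0% or 74.0% and is excluded. The completer with a full first bottle and a lost second has bounds 38/73 = 52% and 100%, so is kept in the main PP set and removed in the repeat.

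Two simpler repairs should be avoided. Dropping the interval from both numerator and denominator gives the last patient 38/38 = 100%, the same false value. Barring every exclusion that involves an unreturned bottle would keep patients whose upper bound is already below 80%.

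The cost is SAP wording and programming. Diary data are self-reported. SAP 9.3 draws on the Drug Log eCRFs only, so the diary must be brought into the compliance dataset. The SAP amendment history lists simplification of this algorithm as intended, and the change gives some of that up.
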